4 STUDY DESIGN

4.1 OVERALL DESIGN

This is a controlled, single-blind, cross-over study design that will enroll 10 subjects suffering from moderate to severe AD with an MMSE of 5-20 and no neuropsychiatric symptoms of dementia. The study is designed to compare the effects of musical intervention consisting of an emotionally impactful tune unique to the subject versus a control intervention consisting of nature sounds.

The study will involve five visits one week apart from each other. The first visit will be a Screening Visit in which informed consent will be obtained, eligibility will be evaluated, an auditory assessment will be administered, and demographics and medical history will be recorded. If eligibility is confirmed, the subject will progress to the Baseline Visit. At the Baseline Visit, the CGIC, SSS, and SIB-8 will be administered, and an interview will be conducted. During the interview, three musical tunes that have a positive meaning to the subject will be identified. After the Baseline Visit and before Visit 1, one tune will be randomly selected out of the three to be used as the experimental intervention.

A randomization program will be used to deliver either the selected musical tune or nature sounds via over-ear headphones at Visit 1. Visit 2, which will occur a week later, will be identical to Visit 1, but the subjects that were originally exposed to music will hear nature sounds and vice versa. Over the course of a 3-hour session during Visit 1 and Visit 2, both interventions will be delivered as 10-minute segments at the top of each hour. After each musical intervention, the subjects will remain in the same research environment and will be free to interact with their caregivers and the staff until the next round of music is performed. The third and final interventional segment will be followed by the administration of the CGIC, SSS, and SIB-8. Finally, at Visit 3, subjects will complete three consecutive 10-minute fMRI scans: resting state (baseline measure), preferred music, and nature sounds, to be administered in a randomized order. The resting state fMRI will serve as the baseline reading. All measures will be done between 9am and 1pm.

4.2 SCIENTIFIC RATIONALE FOR STUDY DESIGN

Our target population for the study is subjects with moderate to severe AD due to the high prevalence of the disease and the fact that this population was the focus of the preliminary reports cited previously^{1,3,4}. The diagnosis of AD will be established using the National Institute of Neurological and Communicative Disorders and Stroke and the Alzheimer's Disease and Related Disorders Association (NINCDS-ADRDA) Alzheimer's Criteria for possible and probable AD²³ and the Diagnostic and Statistical Manual of Mental Disorders, Fifth Edition (DSM-V) per clinical assessment by the PI or another qualified investigator during the Screening Visit.

All research examined clearly states that brain activation via music depends on the type of music that is chosen¹. This research established that the most effective type of music will be highly individual (AARP GCBH Meeting personal communication). The music to be selected will be different for each subject and will have a special, emotional connection (positive) to the individual participating in the study. Therefore, during the Baseline Visit, the patient's caregiver, as well as the subject, will be interviewed to establish the subject's three favorite tunes. One of the identified tunes will be randomly selected to use as the experimental intervention. Each 10-minute musical exposure will be the same for the unique subject on a given day as described above and the tune will be consistently administered to the subject both during the clinical stimulation and the fMRI scans.

The CGIC will be the primary outcome measure, the SSS will be the key secondary outcome measure, and the SIB-8 will be an exploratory measure. We have chosen the CGIC in an attempt to evaluate the overall clinical impact of music. Secondly, we have chosen the SSS, which has been validated to evaluate level of arousal in this population. Finally, we have chosen the SIB-8 to explore the potential cognitive effect in this population, since it is a validated scale developed specifically for patients in the moderate to severe stages of the disease. The SSS and the SIB-8 have the ability to show changes in short periods of time.

Auditory acuity will be evaluated to determine the intensity of the sound the subjects are exposed to. Specifically, the level of sound the subjects are exposed to will be calibrated in relation to their hearing abilities in order to assure a similar level of music stimulation in all subjects. We will use a well-established hearing test, pure-tone audiometry, to perform this evaluation on the study population²⁴.

The goal of the fMRI scans is to determine whether the preferred music intervention enhances connectivity with brain networks associated with arousal as compared to pure resting state and nature sounds. The primary outcome measure for connectivity will be a measure of entropy or spread of information from the auditory cortex to other parts of the brain.

Our chosen MMSE score for the study is 5-20 points. The MMSE is a test designed to evaluate basic cognitive functions and is often utilized to gauge the level of impairment in patients with AD. The MMSE is scored is 0-30, with scores of 20 to 24 suggesting mild dementia, scores of 13 to 20 suggesting moderate dementia, and scores of less than 12 suggesting severe dementia.

On average, the MMSE score of a person with AD declines about two to four points each year. As stated, a MMSE score of 20 usually reflects a patient in the moderate stages of the disease where brain degeneration starts to become more pronounced, but where we believe auditory areas remain almost intact. The lower score of 5 reflects the severe stages of the disease where we believe even auditory areas of the brain engaged in music activation will start to be affected, thus scores below 5 will be excluded.

4.3 JUSTIFICATION FOR TREAMENT INTENSITY

In our experience, a minimum of 10 minutes of music stimulation is required to generate an effect. We have observed in our clinical practice the effects of music stimulation in this population start to decline when music is ceased. The effects continue to decrease for approximately 3 hours, at which point we expect the effects will subside entirely. We therefore designed this study to provide music stimulation in 10-minute increments spread across 3 hours to observe if the intermittent stimulation either overlaps (and creates a "dose" increase) or prevents a decline in the effect.

4.4 END OF STUDY DEFINITION

A participant is considered to have completed the study if he or she has completed all visits of the study as outlined in the SoA, Section 1.3.

The end of the study is defined as completion of the last visit in the SoA.

5 STUDY POPULATION

5.1 INCLUSION CRITERIA

In order to be eligible to participate in this study, an individual must meet all of the following criteria:

- 1. Provision of signed and dated informed consent form
- 2. Person of any sex/gender aged between 55 and 90
- 3. Stated willingness to comply with all study procedures and availability for the duration of the study
- 4. In the opinion of the investigator, has an informant able and willing to provide accurate information about the participant (may be paid or unpaid caregiver)
- 5. Suffer from moderate to severe AD as established by the study team using the NINCDS-ADRDA Alzheimer's Criteria for possible and probable AD
- 6. Diagnosis of AD or other type of dementia as defined by the DSM-V
- 7. MMSE score of 5-20
- 8. Subject is reported by the study partner to be able to listen to a minimum of 10 minutes of music and a sound in an uninterrupted manner.

5.2 EXCLUSION CRITERIA

An individual who meets any of the following criteria will be excluded from participation in this study:

- 1. Suffer from severe hearing impairment as reported by the informant
- 2. Lack of ability to tolerate the intervention or the participation in the fMRI portion of the study
- 3. Presence of neuropsychiatric symptoms of dementia as determined by clinical observation by the PI, including history of agitation and/or combative behavior.
- 4. Individuals who score ≥ 12 seconds on the TUG Test.

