2.3 RISK/BENEFIT ASSESSMENT

2.3.1 RISKS TO SUBJECTS

PHYSICAL

Risks associated with increased activity

During the clinical stimulation of the brain using an emotionally impactful musical tune, increased level of arousal and increased desire to move due to music stimulation may result in an increase in a subject's physical activity potentially causing injuries or falls if adequate supervision is not provided.

Risks associated with auditory stimulation

The auditory system may be affected if the experimental music intervention or the control consisting of nature sounds is provided at excess volume.

Risks associated with fMRIs

fMRIs are made without using any ionizing radiation, so subjects are not exposed to the harmful effects of ionizing radiation. But while there are no known health hazards from temporary exposure to the fMRI environment, the fMRI environment involves a strong, static magnetic field, a magnetic field that changes with time (pulsed gradient field), and radiofrequency energy, each of which carry specific safety concerns:

The strong, static magnetic field will attract magnetic objects (from small items such as keys and cell phones, to large, heavy items such as oxygen tanks and floor buffers) and may cause damage to the scanner or injury to the subjects or medical professionals if those objects become projectiles. Careful screening of people and objects entering the fMRI environment is critical to ensure nothing enters the magnet area that may become a projectile.

The magnetic fields that change with time create loud knocking noises which may harm hearing if adequate ear protection is not used. They may also cause peripheral muscle or nerve stimulation that may feel like a twitching sensation. The radiofrequency energy used during the fMRI scan could lead to heating of the body.

Some subjects find the inside of the fMRI scanner to be uncomfortably small and may experience claustrophobia²².

PSYCHOLOGICAL

Risks associated with assessments and questionnaires

Memory and cognitive testing may cause some individuals to become upset, frustrated, or tired. All participants have the right to decline to answer any questions and may ask to stop testing at any time for any reason.

PRIVACY

Risks associated with loss of confidentiality

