8.2 SAFETY AND OTHER ASSESSMENTS

NINCDS-ADRDA Alzheimer's Criteria for possible and probable AD research diagnosis

• The PI or another qualified investigator will apply the NINCDS-ADRDA Alzheimer's criteria to make a research diagnosis of the subject's AD status as possible or probable AD.

Diagnostic and Statistical Manual of Mental Disorders, Fifth Edition (DSM-V) research diagnosis

• The PI or another qualified investigator will apply the DSM-V criteria to make a research diagnosis of the subject's AD status.

Mini-Mental State Exam (MMSE)

 The MMSE will be performed with the subject and assesses orientation, immediate and delayed recall, concentration, language, and construction skills on a 0-30 scale of correctness. An MMSE score between 5-20 indicates subject eligibility.

Auditory Assessment

 An audiologist will perform pure-tone audiometry, where the subject will be instructed to raise their hand (or point to the appropriate ear) when they hear a tone.

Vital signs

• Vital signs (i.e. sitting pulse and sitting blood pressure) will be obtained by trained study personnel.

Timed Up and Go (TUG) Test

 The TUG Test measures the time (in seconds) taken for an individual to stand up from a standard armchair, walk 10 feet, turn, walk back to the chair, and sit down. It is a commonly used scale for measuring functional mobility and risk of falls.

MRI Metal Screening Questionnaire

• The MRI Metal Screening Questionnaire will be performed to determine if the subject has any metal items in their body that may be harmful in the scanner or may interfere with the MRI examination.

Recording of AEs and SAEs

See Section 8.4 for AE and SAE recording and classification.

Assessment of intervention adherence

 A compliance assessment will be recorded at Visit 1, Visit 2, and Visit 3. The duration of time that the subject adheres to the established procedures of the intervention will be logged during each visit on a CRF.

Functional Network Analysis

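### Severe hearing impairment is decided by informant report alone, although audiometry planned for every subject at Screening could decide it before randomisation

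*Combined protocol and SAP*

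**What the plan says.** Section 5.2, exclusion 1: "Suffer from severe hearing impairment as reported by the informant". No other source is named, severe is not defined and there is no audiometric cut-off.

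Section 8.2, Auditory Assessment: "An audiologist will perform pure-tone audiometry, where the subject will be instructed to raise their hand" or point to the ear on hearing a tone. The schedule of activities puts this assessment at Screening. Section 4.1 describes that visit as the one at which "eligibility will be evaluated, an auditory assessment will be administered, and demographics and medical history will be recorded". The schedule places randomisation at the following visit, Baseline.

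Section 4.2 gives the test one purpose: "Auditory acuity will be evaluated to determine the intensity of the sound the subjects are exposed to". The level is to be "calibrated in relation to their hearing abilities in order to assure a similar level of music stimulation in all subjects".

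Section 2.3.1 lists a related risk: "The auditory system may be affected if the experimental music intervention or the control consisting of nature sounds is provided at excess volume".

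Section 8.1, Eligibility Criteria, names the interview with subject and informant, medical records and the MMSE as the means of establishing eligibility. Audiometry is not among them.

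**The concern.** The intervention and its control both work through hearing, as does the fMRI measure of interest, the diversity coefficient of the auditory cortex (Section 9). The protocol uses measured cut-offs for other traits: MMSE 5-20 (Section 5.1) and 12 seconds or more on the TUG (Section 5.2). For hearing it obtains a measurement at the same visit and then decides eligibility on a third party's report.

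Two things are at stake if the informant misses a severe loss that the audiogram shows. If calibration tries to compensate, the output moves towards the volume risk that the protocol itself names. If it cannot compensate, the subject hears neither sound adequately and adds little to the contrast. Section 9 intends the model estimates for the design of a later, more definitive trial, so any attenuation would be carried into that design.

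**Working it through.** The documents state no figure to reproduce. The check is a reading of the sections against each other, followed by one line of arithmetic.

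**Does any rule make the audiogram count for eligibility?**

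| Place | What it covers | Does it use the audiogram? |
|---|---|---|
| 5.2, exclusion 1 | Severe hearing impairment | No, informant report |
| 5.1, inclusion 8 | Able to listen for 10 minutes without interruption | No, study-partner report |
| 5.2, exclusion 2 | Tolerance of the intervention and fMRI | No; headphones can be tolerated by someone who hears little |
| 8.1, Eligibility Criteria | Interview, records, MMSE | Not listed |
| 6.3 | Headphones in place for 10 minutes while sound plays | No; a subject who hears nothing is recorded as compliant |
| 7.2 | Withdrawal when an exclusion criterion is recognised late | Only through exclusion 1, hence the informant |
| 4.2 | Setting the sound level | Yes, for level only |

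The omission in Section 8.1 is weak evidence by itself, because that list also leaves out the TUG, which is an exclusion criterion. The wording of exclusion 1 settles the matter. Nothing says who decides when audiogram and informant disagree.

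**What happens to the estimate?** Hearing is fixed within a subject over Visits 1 and 2, so its main effect cancels from the music-versus-nature contrast. It matters only if it changes the response to sound, and the Section 9 models contain no hearing term. Let n = 10, let k subjects have a music-minus-nature difference of zero, and let the others share a true difference δ. Then

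mean difference = ((n − k) / n) × δ

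- k = 0: (10/10)δ = δ, no change.
- k = 1: (9/10)δ = 0.90δ, a fall of 10%.
- k = 2: (8/10)δ = 0.80δ, a fall of 20%.

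This uses the plain average of the ten differences. With complete data, that is what a model with sequence, period, intervention and random subject effects gives when the two sequences are of equal size. The values of k and the zero effect are assumptions. The documents give no rate of unreported hearing loss, no effect size and no standard deviation.

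**Is the information available in time?** Yes. The schedule shows the auditory assessment at Day 1 and randomisation at Day 7.

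**The case against.** The best counter-argument is that calibration already answers variation in hearing: if it works, all subjects receive similar stimulation and nothing is diluted. On that view the two harms contradict each other. They are in fact alternatives. Either the level is raised enough, which brings in the volume risk, or it is not, which brings in dilution. It does stand that both cannot apply fully to the same subject, and that calibration limits the gap to severe loss.

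Other safeguards also make the case narrow. The informant must be judged able to give accurate information (inclusion 4), the study partner spends 10 hours or more a week with the subject, inclusion 8 bears on functional listening, and subject and caregiver are interviewed about tunes at Baseline. An investigator might well stop such a subject. None of these uses the audiogram, so the gap is narrow but open.

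Three stronger readings are tempting, and the documents do not support them:

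- A reader might infer that such a subject will be enrolled and played louder sound. The text shows only that enrolment is possible. Louder output is an inference from the calibration rule, which does not say it.
- A reader might take 10% or 20% as the expected loss of effect. The documents give no basis for any number of affected subjects, and that number may be zero.
- A reader might treat inability to complete audiometry as inability to hear, and exclude on it. At the low end of MMSE 5-20, failure to signal may be cognitive. Such an exclusion would fall on the more impaired subjects whom Section 4.2 deliberately includes.

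The opposite error, excluding a subject whom the informant wrongly calls severely impaired, costs a recruit but does not bias the within-subject contrast.

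**Conclusion.** The point holds as a cheap improvement. Exclusion 1 can admit a subject whose own Screening audiogram shows severe loss, because the only stated source is the informant and the audiogram has no stated role beyond setting the level. That conclusion rests on the text and is firm.

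The size is not firm. One affected subject is 1/10 of the planned sample. If that subject has no effect and sequences are equal, the mean difference falls by 10%. How many subjects would be affected cannot be derived from the documents. In a pilot of n=10 meant for estimation, this is a reason to tidy the criterion and does not undermine the design.

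**What to change.** Reword exclusion 1 so that severe hearing impairment is determined by the Screening pure-tone audiogram. The trial audiologist should set the cut-off before enrolment. The informant's report becomes supporting history, and the basis for the decision only when no usable audiogram is obtained.

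Reconcile Sections 4.2, 5.2, 8.1 and 8.2 so that they agree on whether the audiogram bears on eligibility and on who decides when it conflicts with the informant.

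Do not exclude subjects automatically for failing to complete audiometry. State instead how their sound level is set, since the calibration in Section 4.2 presupposes a result.

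Rewording exclusion 1 does not settle the volume question for subjects with lesser loss. Section 4.2 states no upper limit on output and should be reconciled with the risk in Section 2.3.1. No cut-off or level is proposed here.

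The cost is a short amendment and possibly an occasional extra screen failure. No new procedure and no change in visit order is needed, because the test already precedes randomisation.

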5.3 SCREEN FAILURES

Screen failures are defined as participants who consent to participate in the clinical trial but are not subsequently randomly assigned to the study intervention or entered in the study

Individuals who do not meet the criteria for participation in this trial (screen failure) because of transient issue(s) may be rescreened one additional time following resolution of these issue(s). Reconsent will be required prior to rescreen.

5.4 STRATEGIES FOR RECRUITMENT AND RETENTION

Recruitment

The PI will contact physicians in the Charleston area to provide them with information about the study and request patient referrals of potential subjects. Once a referral has been made, the potential subject will be contacted by

the PI by telephone, the study will be described, and if the subject and study partner express interest in the study, the study coordinator scheduled for a screening visit.

Retention

Due to the short duration of the study, issues with retention are not anticipated.

6 STUDY INTERVENTION

6.1 STUDY INTERVENTION(S) ADMINISTRATION

6.1.1 STUDY INTERVENTION DESCRIPTION

This is a randomized, cross-over study to measure global and clinical impact and level of arousal in subjects suffering from moderate to severe AD when exposed to emotionally impactful music compared to control intervention. In partnership with the study partner (a person who spends 10 hours or more a week with the subject and can reliably report on the subject's condition), three tunes will be chosen for the purposes of the study. The tunes chosen will need to be related to a past meaningful, positive experience of the subject, as determined by the subject and the subject's study partner. The pieces will be restricted in duration to between 1.5 and 2 minutes each. A piece will be chosen at random and will be saved on a portable device, and subjects will be asked to listen to the melody using high quality (Bose), over-ear headphones. The total exposure time will be 10 minutes each hour over a three-hour period. The melody will be repeated as many times as necessary to complete the 10-minute period. The control intervention will involve listening to nature sounds at the same duration and administration scheme. fMRI will be used to identify how brain networks are modulated via exposure to this music and how they associate with the clinical findings.

6.1.2 DOSING AND ADMINISTRATION

Over the course of 3-hour sessions at Visit 1 and Visit 2, either the musical intervention or the control intervention consisting of nature sounds will be delivered as 10-minute segments at the top of each hour.

6.2 TO MINIMIZE BIAS: RANDOMIZATION AND BLINDING

The researcher responsible for randomization will design, implement, and maintain randomization procedures. A software system will generate study assignment. When a treatment assignment is generated, a sound identification number will not be chosen in sequence from the treatment file but rather from the next sequential assignment in the master randomization scheme. Thus, treatment assignment is unpredictable to clinical center staff.

This is a single-blind, randomized, cross-over study with raters being blinded to the specific intervention (music or nature sounds) that the subjects receive. The study team will be instructed on the importance of maintaining the blind and special measures will be put in place to avoid inadvertent unblinding. Raters will be unaware if the subjects receive either music or nature sounds. Music will be provided through over-ear headphones to prevent the raters from hearing the intervention being administered and the evaluation will be performed after the intervention is complete.

